Number of anticipated enrolling sites updated to 14	Study underway with most sites activated	Protocol Summary
Sample size calculation clarified, including basis for assumptions of primary outcome rate in each group; clarified that test is one-sided and therefore reduced alpha from 0.05 to 0.025. Statistical analysis now clearly specifies 97.5% one-sided confidence intervals will be constructed for difference between groups.	This is a superiority study for primary outcome so one-sided test more appropriate (no change in sample size resulted from this modification). Justification for superiority design provided under Statistical methods .	Sample size; Statistical methods
Sample size / power estimate for safety outcome (recipient graft survival at 30-d) refined; baseline rate justified at 96% based on updated SRTR data, modified non-inferiority margin from 10% to 6% and set one-sided alpha at 0.025. This resulted in larger required sample size of 336 recipients for 80% power. Calculation provided for expected number of recipients (n=320) based on revised 40% expectation of proportion of hearts transplanted	More stringent non-inferiority margin based on feedback suggesting 90% as lower limit of acceptable graft survival; changed one-sided (non-inferiority) alpha to 0.025 for more stringent testing of NI. Updated data on proportion of hearts transplanted expected in this donor population led to revised estimate of number of recipients for this analysis.	Sample size; Statistical methods
No longer plan for statistical comparison of baseline variables between study groups; instead we now pre-specify important covariates for adjustment of the primary outcome (age, blood group). Primary analysis remains with chi-square test but include subsequent multivariable model adjusting for age and blood group.	The CONSORT statement on reporting RCTs recommends against comparing baseline variables between groups (as all differences will be chance imbalances occurring despite randomization). Instead adjustments should be prespecified based on relevant prognostic variables.	Statistical methods
Site will be included as a random effect in the multivariate model for outcomes (primary outcome and secondary outcomes)	Randomization is stratified by site and imbalances in sample size and rates of hearts transplanted are expected between sites. Therefore, site should be included as a random effect in the model.	Statistical methods

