Endpoints	
The primary outcome is the proportion of hearts transplanted (the number of hearts transplanted divided by the total number of potential donors).
 
The safety outcome is proportion of hearts transplanted that maintain graft function at 30-days and 1-year.
 
Secondary outcomes will include: 1) time from randomization to weaning off vasopressors: defined as being off all vasoactive agents (except for vasopressin); 2) proportion weaned off vasopressors by 12-hours (same criteria as #1); 3) time achieving hemodynamic stability adequate to order first echocardiograph; 4) left ventricular ejection fraction measured on first donor echocardiography; 5) total number of organs transplanted

Population	We plan on enrolling 800 brain dead organ donors with authorization for donation and research in order to have 752 evaluable subjects who receive the study drug or placebo
Phase	Three
Number of Sites	Est. 14 OPOs, 1 coordinating site for human (recipient) data
Study Duration	18-24 months

Abbreviations

AOPO, Association of Organ Procurement Organizations

BD, brain dead

DSMC, data and safety monitoring committee

LVEF, left ventricular ejection fraction

OPO, organ procurement organization

ODRC, Organ Donation Research Council

OPTN, Organ Procurement and Transplant Network

SRTR, Scientific Registry of Transplant Recipients

T4, thyroxine

TTE, transthoracic echocardiography

UNOS, United Network for Organ Sharing

Administrative information

Title {1}	A Multicenter Randomized Placebo-Controlled Trial of Intravenous Thyroxine for Heart-Eligible Brain Dead Organ Donors
Trial registration {2a and 2b}.	Clinicaltrials.gov NCT04415658. Registered June 4, 2020. https://clinicaltrials.gov/ct2/show/NCT04415658
Protocol version {3}	3.0
Funding {4}	None (internal administrative support provided by Mid-America Transplant)
Author details {5a}	[name], Washington University in St. Louis School of Medicine [name], Mid-America Transplant
Name and contact information for the trial sponsor {5b}	Mid-America Transplant [name]
Role of sponsor {5c}	Mid-America Transplant will not have any role in the design or analysis of the trial data. They will not have any role in the writing of the manuscript or the decision to submit the report for publication.

Introduction

Background and rationale {6a}

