Primary: Intravenous thyroxine (T4) will increase the proportion of hearts transplanted when given early after brain death to heart-eligible hemodynamically unstable potential organ donors

Safety: Hearts transplanted from donors receiving T4 will have non-inferior graft survival to those from the placebo group at 30-days

Secondary: T4 will reduce time to wean off vasopressors and improve cardiac ejection fraction

Trial design {8}

Randomized in parallel groups to intravenous thyroxine or saline placebo in 1:1 ratio

Randomization will be in blocks, stratified by OPO site, allowing each site to serve as its own control (given heterogeneity in donor management protocols between OPOs)

Administration of study drug or placebo will not be blinded

Methods: Participants, interventions and outcomes

Study setting {9}

This study will be performed under the auspices of various Organ Procurement Organizations (OPOs) across the country (list of active sites available on clinicaltrials.gov). Participants will be patients already declared dead by neurologic criteria (i.e. brain dead) and who have provided authorization (first-person or by living surrogates) for both organ donation and for research. They may be physically located either/both in the hospitals in which they were declared and/or at an independent recovery/donor management facility of the OPO. The donor component has been deemed not to involve human subjects research and participating hospitals and OPOs are therefore not engaged in human subjects' research. The coordinating site (Washington University in St. Louis) will be the research site responsible for collecting recipient outcome data. A waiver of consent has been obtained for de-identified collection of this human recipient data.

Eligibility criteria {10}

Inclusion Criteria:

1. Declared dead by neurologic criteria
2. Provided authorization for organ donation and for research
3. Donor age of 14-55 years (inclusive) and weight \geq 45 kg (100 lbs)
4. On one or more vasopressor and/or inotropes (not including vasopressin)

Exclusion Criteria:

1. Brain death declared $>$ 24 hours prior
2. Known CAD or MI (by history, EKG, or previous cardiac cath)*
3. Significant valvular heart disease (by history of echo)*
4. Prior sternotomy or cardiac surgery*
5. Donor at VA hospital
6. Received intravenous or oral thyroid hormone in the past month
7. Known HIV+ status

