8. Additional outcomes routinely collected from heart transplant recipients will also be aggregated and analyzed, including need for post-transplant mechanical circulatory support and other measures of primary graft dysfunction

Safety endpoints:

The following adverse events will be prospectively collected on all study donors. All events deemed either related or potentially related to the study drug infusion will be reviewed by the site coordinator. Any serious related events (defined as hemodynamic instability leading to cardiac arrest or donor loss prior to organ recovery) will be forwarded to the DSMC for additional review:

1. Severe hypertension (systolic BP > 200 mm Hg)
2. Tachycardia (HR > 150 and increased more than 20 over baseline)
3. New/worsened tachyarrhythmia (SVT, Atrial fibrillation, Ventricular tachycardia or fibrillation)
4. Cardiac arrest or any donor loss prior to the OR
5. Fever – new, above 102 degrees Celsius
6. New skin rash

Participant timeline {13}

Sample size {14}

The proportion of potential heart donors who were able to provide a heart for transplantation in our pilot studies was between 30-60% (12, 14), a rate concordant with the recent literature (23). Proposed effect sizes of thyroid hormone treatment have ranged as high as an absolute increase of 20% or more in proportion of hearts transplanted in non-randomized studies (24); a large retrospective analysis of UNOS data found that those who received thyroid hormone (57% of 40,124 donors) had more hearts transplanted (7). The increase was from 25.8% without treatment to 35% with thyroid hormone (among all donors, not only those who were strictly heart-eligible, as required in this study). Based on our pilot data and this literature, we propose an absolute treatment effect size of 10% as the threshold for this study. In order to detect an increase in the proportion of hearts transplanted from 35% to 45%, we will need 752 total donors (376 per group), assuming 80% power and a one-sided alpha of 0.025. Because we expect some loss of donors after enrollment (e.g., clinical issues that interrupt adherence to the protocol), we will enroll a total of 800 donors (400 in each study group).

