For our safety analysis in recipients of donor hearts, we have calculated a sample size necessary to demonstrate non-inferiority in graft survival. Based on recent data provided by SRTR, the expected 30-day graft survival after heart transplantation is 96%. We will test for a decrease of no greater than 6% in graft survival (i.e. from 96% to 90%; see *Statistical Methods* for a full explanation of assumptions and testing). With one-sided alpha of 0.025, we would need 336 recipients (168 per group) to have 80% power to exclude such a difference. Therefore, based on our sample size of 800 donors and an expectation that overall at least 40% of donor hearts will be transplanted, we expect a minimum of 320 recipients for this analysis; this sample size will provide a power of 78% for non-inferiority. It is likely that more than 40% of hearts will be transplanted; in fact, we saw in excess of 50% of hearts transplanted in our pilot data. Therefore we expect to have more than the required number of recipients to achieve 80% power. This sample size of recipients would also provide 80% power to demonstrate non-inferiority at the one-year survival endpoint.

Recruitment {15}

There are between 50 and 100 heart-eligible organ donors per year managed at most OPOs (of variable sizes) around the country. Therefore we are recruiting at least 10 OPO sites (est. 50 participants per OPO per year) in order to complete recruitment of adequate donors (n=800) within a 18-month study period.

Assignment of interventions: allocation

Sequence generation {16a}

A random sequence of 1s and 0s will be computer-generated by the central coordinating site in blocks of 30 for each participating OPO site (i.e. stratified by site). A web-accessible randomization sheet will be provided to each site with three such blocks (i.e. randomization key for 90 potential subjects).

Concealment mechanism {16b}

Only once eligibility has been confirmed will the on-site organ procurement coordinator will login to the website with the randomization list and determine (using the next available row) to which group the donor has been assigned. The coordinator will enter the UNOS# of the donor on the randomization form, as well as

the time and date of enrollment in the study before communicating the study assignment to OPO staff. The site study coordinator will review the randomization log to ensure that all eligible donors are being randomized and that sequential randomization rows are utilized.

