Implementation {16c}

Randomization sequence of T4 vs. saline will be generated by the central coordinating statistician.

Participants will be enrolled by the organ procurement coordinators at each site managing the donor after determining eligibility. They will determine the allocation to one of the study groups and assign participants to their randomized intervention.

Assignment of interventions: Blinding

Who will be blinded {17a}

Care providers will not be blinded to study groups. Organ donors (being deceased) will be unaware of treatment. Assessment of cardiac function on echocardiography will also be blinded to study group.

Procedure for unblinding if needed {17b}

The study will not be blinded to coordinators or to those performing organ allocation (e.g. transplant surgeons). Furthermore, we will ensure that it is clearly documented in DonorNet that each participant is enrolled in this study. Each participant can also receive open-label T4 at the termination of the 12-hour study period, at the discretion of the physician or study team.

Data collection and management

Plans for assessment and collection of outcomes {18a}

Each OPO will identify a site study coordinator who will be responsible for ensuring proper completion of data collection forms. The central coordinating OPO will create the data collection forms and distribute them to each study coordinator (data collection forms provided in Appendix). The central coordinating statistician will train each study coordinator on data collection and data entry procedures. *Recipient data will be collected by the central site by matching donor UNOS IDs to the SRTR database of recipient and graft outcomes. No identifiable data on recipients will be collected and this data will not be shared with the sites.*

Plans to promote participant retention and complete follow-up {18b}

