No participants will be lost to follow-up as the final assessment occurs at organ recovery, which is available for all donors. However, it is possible that some donors may have incomplete data or may not finish the protocol once it is started. For example, a donor may be authorized for donation but may not become an organ donor ('authorized, not recovered' status). Such a donor does not undergo organ recovery and so will not have data at the final endpoint. However, we will analyze groups as randomized, i.e. by intention-to-treat, imputing these non-recovered donors as not having hearts transplanted. Similarly, we will analyze all those randomized to T4 within that study group even if they do not receive the drug or have it discontinued before 12-hours.

Data management {19}

Study-specific data will be entered onto a paper data flowsheet (Appendix A) with the UNOS ID for each

participant and the assigned group marked at the top. This data sheet will be forwarded to the site study coordinator who will enter participant data into a secure REDCap database. This has built-in data validation and range checks. This study data will be supplemented by matching each enrolled donor (by UNOS ID) to their SRTR demographic data. This includes donor age, sex, and other important variables. The central coordinating statistician will perform data quality checks monthly and will work with the study coordinators at each OPO to resolve any quality issues.

Confidentiality {27}

No participant data will be shared outside of the study except when UNOS IDs are provided to the OPTN/SRTR to acquire data on whether transplanted hearts functioned and recipients survived. No recipient identifying data will be collected.

Plans for collection, laboratory evaluation and storage of biological specimens for genetic or molecular analysis in this trial/future use {33}

No biologic specimens will be collected for this trial or for future use.

Statistical methods

Statistical methods for primary and secondary outcomes {20a}

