We will present descriptive statistics for demographic and clinical variables, including by study group, but will not perform statistical comparisons of differences between study groups for baseline variables that should be balanced by randomization. We will first evaluate the primary outcome, the proportion of hearts transplanted, presenting the absolute and relative differences between the study groups, along with 97.5% one-sided confidence intervals. For our primary analysis, we will test the association between treatment and proportion of hearts transplanted, using a one-sided chi-square test at significant level of 0.025. Then we will proceed to a multivariate model that adjusts for potentially confounding variables and random site effect. The SRTR registry has developed comprehensive organ-specific risk-adjustment models (25). Older age and blood group are consistently the most important variables impacting whether hearts are transplanted. For this reason, we will include age and blood type as relevant pre-specified covariates. Since randomization was stratified by site, and imbalance in sample size across sites are expected, we will also include site as a random effects in our multivariate model. This will provide subject-specific measures of treatment effect, in terms of a conditional effect size and adjusted odds ratio (with 97.5% one bound confidence interval).

Given that a systematic assessment of non-randomized studies using T4 for heart donors has suggested an improved rate of hearts transplanted, while prior small randomized studies have suggested no effect (i.e. no studies suggesting that T4 therapy results in worse heart outcomes) (10), we have selected a superiority design as most appropriate for our primary outcome. We are seeking to ascertain whether the addition of T4 infusion to standard donor care results in more hearts transplanted. Therefore, our null hypothesis is that T4 treatment results in an equal or lower rate of hearts transplanted, meaning our alternate hypothesis is that T4 treatment is superior to no treatment. If the null hypothesis were not excluded, there would be no rationale to use T4 in addition to standard donor management and no benefit to focusing on a two-sided test evaluating whether it was worse than placebo. Therefore statistical tests will be one-tailed at a stringent significance

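### The primary test pools across OPOs and ignores age and blood group: it is valid but gives up modest precision, and no adjusted risk difference is planned

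*Combined protocol and SAP*

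**What the plan says.** All references are to the combined protocol and SAP, v3.0.

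- **Primary test.** Statistical methods {20a}: "For our primary analysis, we will test the association between treatment and proportion of hearts transplanted, using a one-sided chi-square test" at 0.025. No strata or covariates are named. The absolute and relative differences, also unadjusted, are presented with 97.5% one-sided bounds. The amendment history confirms that the chi-square was kept as primary in v3.0.
- **Adjusted model.** It comes afterwards, with age, blood type and a random site effect. Its outputs are subject-specific: a conditional effect, whose scale is not stated, and an odds ratio.
- **Stratification.** Trial design {8} describes randomisation as "stratified by OPO site, allowing each site to serve as its own control (given heterogeneity in donor management protocols between OPOs"). Sequence generation {16a} uses blocks of 30 within each OPO. The Protocol Summary gives the number of sites as "Est. 14 OPOs, 1 coordinating site for human (recipient) data".
- **Expected heterogeneity.** Amendment history: "Randomization is stratified by site and imbalances in sample size and rates of hearts transplanted are expected between sites". Section {20a} ranks age and blood group as the leading predictors of whether a heart is transplanted.
- **Design target.** Sample size {14}: "we propose an absolute treatment effect size of 10% as the threshold for this study".

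**The concern.** The plan gives its own reasons for accounting for OPO, age and blood group, but applies them only to a follow-up model and not to the test that decides the trial. A pooled test does not use each site as its own control, although {8} gives that as the purpose of stratifying. Two things are at stake.

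1. **Precision.** If these factors predict heart use, as the plan says, the primary p-value and bound are wider than the data already collected allow.
2. **Scale.** The trial is designed around an absolute difference. The adjusted result will be a conditional odds ratio, which cannot be set directly against that target.

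**Working it through.** **Step 1: reproduce the plan's sample size.** Inputs from Sample size {14}: 35% vs 45%, one-sided 0.025, 80% power, 1:1. Pooled-variance formula without continuity correction:

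n per group = [z(0.975)·√(2·p̄·q̄) + z(0.80)·√(p0·q0 + p1·q1)]² / d²

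= [1.960·√0.48 + 0.842·√0.475]² / 0.10² = (1.358 + 0.580)² / 0.01 ≈ 376.

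That is 752 in total, as stated. Power is 80.0% at 376 per group. At 400 per group it is Φ[(0.10·√400 − 1.358)/√0.475] = Φ(0.932) = 82.4%. The sample size therefore matches the unadjusted test.

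**Step 2: why the pooled test is valid but slightly conservative.** The pooled variance p̄q̄ contains the between-site variance of the rates, which blocking within site largely removes from the treatment comparison. As a first-order guide, a site SD of s on the logit scale gives a between-site share of (s·0.24)²/0.24 at p̄ = 0.40. For s = 0.3, 0.5 and 0.7 this is about 2%, 6% and 12%.

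**Step 3: simulated power at 800 donors.** The documents quantify neither site variance nor covariate effects, so these are assumptions:

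- 14 OPOs of 13 to 102 donors, blocks of 30.
- Site SD 0.3 to 0.7 (logit).
- Age effect −c per SD and non-O blood group effect −c, with c from 0.3 to 0.6; groups O/A/B/AB 48/37/11/4%.

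Tests compared:

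- Pooled chi-square.
- Cochran-Mantel-Haenszel (CMH) by OPO.
- Standardised risk difference: logistic model with treatment, OPO, age and blood group; average of predicted risk under T4 minus under placebo over all donors; influence-function standard error with an n/(n−p) correction; sparse-site fallback as given under the change below.

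There were 12,000 trials per row, so the Monte Carlo SE of each power figure is about √(0.83·0.17/12,000) = 0.3 points.

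| Site SD, c | Chi-square | CMH | Standardised |
|---|---|---|---|
| none | 82.3 | 82.1 | 82.2 |
| 0.3, 0.3 | 83.0 | 83.1 | 84.2 |
| 0.3, 0.6 | 82.7 | 82.9 | 86.4 |
| 0.5, 0.3 | 83.2 | 84.4 | 85.5 |
| 0.5, 0.6 | 83.1 | 84.0 | 87.5 |
| 0.7, 0.3 | 83.6 | 86.0 | 86.8 |
| 0.7, 0.6 | 83.7 | 85.5 | 88.4 |

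Gains over the chi-square where effects exist: CMH 0.1 (83.1 − 83.0) to 2.4 (86.0 − 83.6) points; standardised 1.2 (84.2 − 83.0) to 4.7 (88.4 − 83.7). With no effects: −0.2 and −0.1, which is noise.

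**Step 4: width.** The distance from estimate to 97.5% bound averages 6.7 percentage points unadjusted, 6.4 to 6.7 for the Mantel-Haenszel risk difference and 6.2 to 6.6 for the standardised one.

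**Step 5: type I error.** One-sided level at a single final look, scenarios with effects, 32,000 null trials at a 40% rate (Monte Carlo SE 0.0009): chi-square 0.0205 to 0.0240, CMH 0.0245 to 0.0251, standardised 0.0247 to 0.0258. The gain does not come from a materially raised level. The interim look was not combined with these levels and is a separate matter.

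**Step 6: independent check.** A second simulation had 4,000 trials per scenario, a single covariate score standing in for age and blood group, and no fallback. For site/covariate log-odds SDs of (0, 0), (0.4, 0.4), (0.5, 0.7) and (0.7, 1.0), it gave chi-square power of 82.1, 82.5, 83.3 and 83.6, CMH 82.0, 82.9, 84.2 and 85.2, and standardised 82.0, 84.3, 87.5 and 91.2. The largest gain was 7.6 points, under stronger effects than in Step 3. In that strongest scenario the standardised analysis rejected 3.2% and 2.7% of null trials at base rates of 35% and 40% (Monte Carlo SE about 0.25 points), so part of that gain may be a slightly high level.

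**Step 7: scale.** The unadjusted odds ratio is (0.45/0.55)/(0.35/0.65) = 1.52. In the scenarios with effects, the same 35% vs 45% appears in the adjusted model as a conditional odds ratio of 1.55 to 1.65. Read naively from a 35% baseline, those give 45.5% to 47.0%, a rise of 10.5 to 12.0 points for a true rise of 10.

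**The case against.** Nothing here is an error. The chi-square is valid with respect to strata and covariates, the trial was sized for it, and v3.0 kept it deliberately while adding the adjusted model. In a randomised trial the unadjusted absolute difference, already planned with its bound, is the quantity Sample size {14} targets, so the target comparison is available. The gain depends on effects that the documents do not quantify, and it is small: at most about half a percentage point on the bound in the main scenarios. The replacement is more complex than a one-line test, and changing a primary analysis during an open-label trial can cost more credibility than a few points of power are worth.

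Most of this stands, and it fixes the grade: an efficiency and reporting point. It does not remove the point. The plan itself asserts that these factors are prognostic, and if they are not, adjusting costs essentially nothing. No adjusted estimate is offered on the design scale, and that gap needs no assumption about prognostic strength. The credibility cost is real; it is why the change is conditional and has an alternative that leaves the primary test alone.

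**Conclusion.** The point holds. The primary test is valid in this respect and consistent with the sample size, but it leaves out the stratification factor and two prespecified predictors. Over the assumed range, the loss at 800 donors is up to 2.4 power points against an OPO-stratified test and 1.2 to 4.7 points against a standardised risk difference, and nil if none of the factors matters. Stronger effects than those assumed would make it larger. The missing adjusted risk difference is a plain reporting gap. The change is advisable rather than essential. Confidence is medium, because the size rests on assumed site and covariate effects.

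**What to change.** In {20a}, take both the primary test at 0.025 and the 97.5% one-sided bound from one analysis that accounts for OPO.

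- **Preferred:** a standardised risk difference from a logistic model with treatment, OPO, age (continuous) and blood group, with a robust variance and a stated fallback driven by donor counts, not outcomes. For example: merge OPOs with fewer than 20 randomised donors, combine groups B and AB, and use the Mantel-Haenszel risk difference if the model still fails. The fallback matters: with all 14 OPO terms, runaway coefficients (any above 8 in absolute value) occurred in 0.1 to 2.6% of simulated datasets at 800 donors, against at most 0.4% with it.
- **Minimum:** a Mantel-Haenszel risk difference with a CMH test stratified by OPO.
- **Either way:** keep the chi-square as a sensitivity analysis and state the scale of the conditional effect.
- **Interim:** if the comparison at 376 donors is to match, use the CMH/Mantel-Haenszel version. The 14-term model had runaway coefficients in 6 to 19% of simulated datasets there.

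**Cost.** No donors or data are added. The cost is credibility. Recruitment began in December 2020 and care is open-label. Implementation {16c} says "Randomization sequence of T4 vs. saline will be generated by the central coordinating statistician", and that statistician also checks data monthly. Data management {19} has each sheet carry the "participant and the assigned group marked at the top". The change therefore needs a documented amendment, made before any comparison of outcomes by group and by people who have seen no such data. If that cannot be assured, leave the chi-square as primary and prespecify the standardised risk difference as the supporting analysis. This closes the reporting gap without touching the primary test.

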level of 0.025. We will also present the effect size with confidence intervals for all outcomes. The analysis will follow an intention-to-treat model. However, we will also perform a secondary per-protocol analysis, including only those receiving at least six hours of study infusion. We will also analyze only those in the placebo group who did not receive open-label T4, for a secondary analysis.

We will analyze the primary safety endpoint of recipient graft survival using a non-inferiority method. Our baseline assumption, based on five-year data (from 2016 to 2020) provided by SRTR, is that 30-day graft survival for hearts will be 96%. We assume this baseline rate for both study groups, as there is no evidence to suggest that graft survival is lower in recipients of hearts from donors administered thyroid hormone. In fact, a recent study suggested treatment was associated with improved graft survival (23). The null hypothesis is that heart graft survival is lower in the T4 treated group by at least a clinically significant margin (set at 6%) compared with that observed in hearts transplanted from the placebo donors. This non-inferiority margin was selected with input of the data and safety monitoring committee (DSMC), including a thoracic transplant surgeon and ethicist. It aligns with that used in other trials assessing graft function after heart transplantation which used similar baseline assumptions (96% graft survival) but allowed more liberal margins (10%) (26). We believe that setting the lower limit of tolerance for this safety analysis at 90% graft survival is most appropriate. We will construct two-sided 95% confidence intervals for the difference in graft survival between the groups, allowing us to test for one-sided non-inferiority at alpha 0.025. This will be performed in the intention-to-treat cohort (i.e. all hearts from enrolled donors, by randomized study group) but we will also evaluate non-inferiority using a per-protocol methodology (i.e. evaluating outcomes in recipients who received hearts from donors who received at least six hours of T4 infusion compared to those who did not).

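### The 80% power at 336 recipients and 78% at 320 hold only for a Wald interval, whose false non-inferiority rate is about 2.7–3.2%; the interval is not named, and a score interval gives about 70–77%.

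*Combined protocol and SAP*

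**What the plan says.** Sample size {14} takes 30-day graft survival as 96% and sets the margin at 6 points (96% to 90%). It then says: "With one-sided alpha of 0.025, we would need 336 recipients (168 per group) to have 80% power to exclude such a difference". With 800 donors and at least 40% of hearts transplanted, it expects a minimum of 320 recipients and adds that "this sample size will provide a power of 78% for non-inferiority". It considers a larger number likely, because more than 50% of hearts were transplanted in the pilot data.

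Statistical methods {20a} gives the true rates behind the power calculation ("We assume this baseline rate for both study groups"), the null hypothesis (survival lower on T4 by at least 6 points) and the decision rule: "two-sided 95% confidence intervals for the difference in graft survival between the groups, allowing us to test for one-sided non-inferiority at alpha 0.025". Neither section says how the interval is to be calculated.

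**The concern.** The interval is the decision rule for the main recipient-safety endpoint. With survival near 96% and 168 recipients per group, about 7 graft losses are expected in each group (0.04 × 168 = 6.7). With so few events, the usual intervals for a difference in proportions do not agree, and the simple Wald interval tends to be too narrow at the non-inferiority boundary. If the sample size was derived from the Wald approximation, the stated power and the stated one-sided 0.025 may not hold together.

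Two things are at stake. One is the rate of false non-inferiority claims, which the amendment history says version 3.0 meant to limit more strictly by setting alpha at 0.025. The other is that the choice of interval stays open in a trial that is not blinded to care providers.

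**Working it through.** **Inputs.** Survival 96% in both groups for power; 90% (T4) versus 96% (placebo) for the error rate; margin 0.06; one-sided alpha 0.025; 336 or 320 recipients (Sample size {14}, Statistical methods {20a}). Planned heart yield 45% versus 35% and 400 donors per group (Sample size {14}).

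**1. Reproducing the plan's figures.** Unpooled normal approximation:

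n per group = (1.960 + 0.842)² × 2 × 0.96 × 0.04 / 0.06² = 7.849 × 0.0768 / 0.0036 = 167.4, rounded up to 168, or 336 in total.

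Power at 160 per group: standard error √(0.0768/160) = 0.02191; 0.06/0.02191 − 1.960 = 0.779; power 78.2%. At 168 per group the same formula gives 80.1%.

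Both stated figures match. The other formulas tried do not: Farrington-Manning (restricted variance) gives 207 per group, and a pooled superiority comparison of 96% with 90% gives 283.

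**2. Exact behaviour of each rule.** For every possible pair of survivor counts, non-inferiority is declared if the lower 95% limit for T4 minus placebo lies above −0.06. The binomial probabilities of those pairs are then summed, at 90%/96% for the error rate and at 96%/96% for power.

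| Recipients (T4/placebo) | Wald: error, power | Farrington-Manning: error, power | Miettinen-Nurminen: error, power |
|---|---|---|---|
| 168/168 (336) | 3.16%, 79.7% | 2.40%, 73.3% | 2.30%, 71.3% |
| 160/160 (320) | 3.07%, 78.2% | 2.34%, 69.6% | 2.34%, 69.6% |
| 189/147 (336) | 2.74%, 80.7% | 2.28%, 77.3% | 2.28%, 77.3% |
| 180/140 (320) | 2.70%, 78.8% | 2.53%, 73.6% | 2.53%, 73.6% |
| 200/200 (400) | 3.12%, 86.1% | 2.36%, 80.7% | 2.36%, 80.7% |

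The unequal rows follow the planned yield: 400 × 0.45 = 180 and 400 × 0.35 = 140, and the same 45:35 ratio applied to 336 gives 189 and 147. A Newcombe interval at 168/168 gives 2.40% and 74.2%.

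**3. Could some other test deliver both at 336?** A linear program found the highest power of any test whose error is at most 0.025 at a grid of points along the null boundary. The ceiling is 74.8% at 168/168 and 77.7% at 189/147, both below 80%.

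**4. Recipients needed with a score interval.** With equal arms, exact power first reaches 80% at 197 per group and stays above it from 199 per group, so 394–398 recipients. That is 49–50% of 800 hearts, against 336/800 = 42% for the stated requirement.

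**5. Can the choice change a conclusion?** Take 168 per group with 9 losses on T4 and 7 on placebo. The difference is −0.0119 and the Wald standard error 0.0232, so the Wald lower limit is −0.0574: non-inferior. The Miettinen-Nurminen lower limit is −0.0624: not shown. If survival is truly 96% in both groups, these two intervals disagree in 8.5% of trials of this size.

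**The case against.** The strongest reply is that the plan nowhere prescribes a Wald interval. Sizing a trial by a normal approximation is common and does not bind the analysis to that interval. This stands. A reader might infer that the trial will test at 3.2%, but the documents do not support that. If a score interval is used, the error stays near 0.025 and only the power is lower than stated. Nor is 336 an arithmetic slip, since it is right by its own formula.

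Second, recipients exist only where a heart was transplanted, so equal arms are expected only if T4 does not change heart yield. Under the planned 45% versus 35%, the Wald excess shrinks to about 0.2 points and score power rises to 77% at 336 and 74% at 320. This also stands, and is why the conclusion is given as a range.

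Third, score intervals are not strictly valid either. At 180/140 their error reaches about 2.8% (Farrington-Manning, placebo survival 94%). The case for them is that they stay close to 0.025 over the plausible range, not that they guarantee it.

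Fourth, 320 is described as a minimum. With 400 recipients score power is 80.7%, so the documents do not support saying that the trial will be underpowered. They support saying that the power attached to 336 and 320 is too high for a test held at 0.025.

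Finally, a Wald error of about 5% can be found at 160/160, but only at 99% placebo survival (5.06%). It is 4.0% at 98% and 2.9–3.3% from 93% to 97%. The planning rate is 96%, so the 5% figure should not be used to describe this trial.

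**Conclusion.** The point holds in a limited form. At the stated 336 recipients, 80% power and a one-sided error of 0.025 are not available together. In equal arms a Wald interval gives about 80% with 3.2% error, and score intervals give 71–73% with 2.3–2.4%. With a 45:35 split the figures are 81% with 2.7%, and 77% with 2.3%. At 320 recipients, score power is about 70% (equal arms) to 74% (45:35), against the stated 78%.

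These results assume 96% survival in both groups for power, 90% versus 96% for error, and independent binomial outcomes. That the Wald approximation was used is inferred from two matching figures, not stated. The statement that both targets cannot be met is limited to 336 recipients: a score interval reaches about 80% at 394–398 in equal arms, which the trial may achieve. The excess error is moderate and does not invalidate the design. The unnamed interval still matters, because it can change the safety conclusion on plausible data.

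**What to change.** In Statistical methods {20a}, name the interval for the difference in graft survival: a score interval, Miettinen-Nurminen or Farrington-Manning. Choose one of the two and fix it before outcomes are compared by group.

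In Sample size {14}, restate the power with that interval as about 71–77% at 336 recipients and about 70–74% at 320, depending on how recipients split between the groups. Add that about 80% needs roughly 395–400 recipients in equal arms, which is about 50% of 800 hearts. Note also that the error stays close to 0.025 but can reach about 2.8% at some placebo survival rates when the arms are unequal.

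The cost is a few sentences and a less favourable stated power. No extra data or change to donor enrolment is needed to make the correction.
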